7 SAFETY MANAGEMENT

7.1 Clinical Adverse Events

Clinical adverse events (AEs) will be monitored throughout the study. See details in section 8.4.1 describing the proactive adverse event surveillance plan.

7.2 Adverse Event Reporting

Since the study procedures are not greater than minimal risk, SAEs are not expected. If any unanticipated problems related to the research involving risks to subjects or others happen during the course of this study (including SAEs), they will be reported to the IRB in accordance with CHOP IRB SOP 408: Unanticipated Problems Involving Risks to Subjects. AEs that are not serious but that are notable and could involve risks to subjects will be summarized in narrative or other format and submitted to the IRB at the time of continuing review.

8 STUDY ADMINISTRATION

8.1 Treatment Assignment Methods

This is a single arm study without randomization or blinding.

8.2 Data Collection and Management

8.2.1 Data sources

8.2.1.1 *Chart review*

Data from chart review will be extracted from the medical record system used at the hospital site. This may include electronic medical records (e.g. the Epic system at CHOP) or paper medical records.

8.2.1.2 *Bedside visual observation “rounds”*

Data will be obtained by visual observing and documenting the current state of respiratory support and physiologic monitoring occurring in patient rooms. See details of COVID-19 modifications in Section 5.3.

8.2.1.3 *Staff questionnaires*

- As listed in Sections 5 and 6

8.3 Confidentiality

All data and records generated during this study will be kept confidential in accordance with Institutional policies and HIPAA on subject privacy. The Investigator and other site personnel will not use such data and records for any purpose other than conducting the study.

The only PHI elements that documented in the study database are the admission date and the date the data collection rounds occurred (which by definition is a date during the patient's hospitalization). Thus this is a *limited dataset*.

The dataset is also *coded* to decrease the risk of breach of confidentiality. A patient-admission ID number not otherwise associated with the individual (not derived from any element of PHI) will be generated by each site and included in the study database allowing patients to be followed over time within the same admission. This is an identifier for each unique patient-admission to allow the data analysis to account for clustering of observations within individual patient-admissions. This is not an actual patient identifier assigned by the hospital; it is a study-specific coded identifier with the linkage master list document held by the individual site (no PHI other than the dates listed above are transmitted to CHOP from other sites).

Hospitals that choose to maintain paper master lists will keep them in locked file cabinets. Hospitals that choose to maintain electronic master lists will store them either on hard drives owned by the institution or servers maintained/approved by their institution. The master list containing the key to decipher the coded dataset will be deleted/destroyed at the earliest possible date that complies with individual hospitals' retention of records policies.

Questionnaire data will not contain any PHI.

No identifiable data will be used for future study without first obtaining IRB approval. The investigator will obtain a data use agreement between provider (the PI) and any recipient researchers (including others at CHOP) before sharing a limited dataset (dates and zip codes).

8.4 Regulatory and Ethical Considerations

8.4.1 Data and Safety Monitoring Plan

The risks of this study are minimal as it involves an intervention intended to align clinical practice with established guidelines and recommendations for quality bronchiolitis care. The Principal Investigator is responsible for data and safety monitoring. The primary risk is breach of privacy and confidentiality. We will also perform proactive surveillance for threats to patient safety.

8.4.1.1 Plan for mitigating and monitoring risk of privacy and confidentiality breaches

CHOP's instance of REDCap will be used for all data collection and management in this study, including data collection performed at non-CHOP sites. For feasibility reasons, study sites will be permitted to use a temporary paper data collection worksheet as long as it is stored in a locked file cabinet and destroyed after abstraction into REDCap. Handling of the master list is described in the above section.

After data collection, exported data for analysis will take place only on computers that meet CHOP IT standards for encryption and password protection as outlined in CHOP IT SOP A-3-6. Data will be stored on the CHOP research SAN and/or other secure servers maintained by CHOP IT. Only investigators and study staff approved by the IRB will have access to data containing PHI.

In accordance with the current CHOP Retention of Records Policy A-3-9 in the Administrative Policy Manual, section on minimal risk human subjects research records, we will retain all information from this study for 6 years after the study is completed, after which PHI will be stripped from the data set.

We recognize that other sites relying on the CHOP IRB have different record retention requirements. For this reason, we will:

1. Provide all data submitted to CHOP back to the Site PI at the conclusion of the study using a CHOP IT approved secure method, allowing each site to meet local record retention requirements. We will not submit Site-Specific Amendments describing each site's record retention requirement.
2. Support other site-specific record retention or local IRB policy exceptions (such as a local requirement to retain data collection worksheets after the data are abstracted into REDCap) that may differ from what we have written above as long as they are described in the Site Survey or a Site-Specific Amendment.

The CHOP PI will monitor and review the study progress, the accuracy and security of the data, and will ensure subject confidentiality and safety.

8.4.1.2 Plan for proactive surveillance for threats to patient safety

In this study, we will regularly evaluate the safety of the intervention, since the intervention may lead to less intensive monitoring for some bronchiolitis patients. In order to monitor for threats to safety, we will:

- Monitor for code blue team activations and rapid response team / medical emergency team / critical assessment team activations in all bronchiolitis patients hospitalized on units participating in the study during the intervention period. This includes patients who were not subjects of data collection, because the intervention is applied at the unit level and could impact the care of patients with bronchiolitis even if they are not reviewed during data collection rounds.
- Investigators will review the chart of each patient meeting the above criteria to determine if the patient was unmonitored at the time of the event that led to the activation.
- Events meeting the activation criteria in which the patient was unmonitored at the time of the event that led to the activation will be considered study adverse events, whether or not they

are related to the research intervention, and be documented in research records as meeting those criteria.

- Investigators will then determine, through chart review and speaking with staff present at the time of the event, if available, if the event was at least possibly related to the study intervention, defined as “there is a reasonable possibility that the adverse event may have been caused by the procedures involved in the research.”
- Investigators will follow the CHOP IRB’s Unanticipated Problems Decision Tree (<https://irb.research.chop.edu/unanticipated-problems>) in order to determine whether the Adverse Event requires prompt reporting to the IRB or should be filed with the next continuing review.
- Adverse Events that meet the definition of Unanticipated Problem Involving Risks to Subjects will be reported promptly to the IRB and the study will be suspended pending review of the event by the IRB. Following the review, we will work with the IRB and staff from the inpatient units to determine if the study should be modified to improve the safety of patients.
- Sites other than CHOP will follow their IRB’s internal reporting requirements, if they differ from the procedures outlined above.

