Schondelmeyer et al evaluated a quality improvement intervention targeting reduction of continuous pulse oximetry in children with bronchiolitis and asthma when they no longer required supplemental oxygen.⁷ Their intervention included staff education, checklists, and electronic health record clinical decision support. They found a reduction of median time on continuous pulse oximetry from 10.7 to 3.1 hours without a difference in rapid response team activations, ICU transfers, or readmissions. This study confirms the safety of the AAP Guideline and Choosing Wisely recommendations, and supports the practice of removing continuous pulse oximetry after supplemental oxygen is discontinued and replacing it with intermittent SpO₂ monitoring.

In a 2017 BMJ expert commentary, "When technology creates uncertainty: pulse oximetry and overdiagnosis of hypoxaemia in bronchiolitis,"¹⁵ Quinonez et al reviewed the literature above and argue that the widespread use of pulse oximetry in stable bronchiolitis patients leads to overdiagnosis of hypoxemia. Overdiagnosis is when a true abnormality is discovered, but awareness of the abnormality does not benefit the patient.¹⁷ The authors conclude that "current body of evidence suggests that we should challenge assumptions regarding the detection and aggressive management of borderline hypoxemia in non-critically ill infants with bronchiolitis," because current overuse of continuous pulse oximetry has led to overdiagnosis of clinically insignificant hypoxemia that contributes to unnecessary resource utilization and risk of patient harm.

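### Proactive safety surveillance is triggered only by emergency-team activations, so an unmonitored child transferred to the ICU without an activation may be missed

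*Combined protocol and SAP*

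**What the plan says.** Section 8.4.1.2 explains that the intervention may lead to less intensive monitoring and undertakes that "we will regularly evaluate the safety of the intervention". It then sets out a sequence:

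- **Trigger.** "Monitor for code blue team activations and rapid response team / medical emergency team / critical assessment team activations in all bronchiolitis patients" on participating units during the intervention period.
- **Population.** All bronchiolitis patients on those units. "This includes patients who were not subjects of data collection", because the intervention acts on the whole unit.
- **Review.** "Investigators will review the chart of each patient meeting the above criteria to determine if the patient was unmonitored" when the event occurred.
- **Study adverse event.** "Events meeting the activation criteria in which the patient was unmonitored at the time of the event" behind the activation, whether or not related to the intervention.
- **Action.** Investigators judge relatedness. An event that meets the definition of an unanticipated problem involving risks to subjects is reported promptly, and the study is suspended pending IRB review.

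Section 7.1 says that clinical adverse events will be monitored throughout, and for the method it says "See details in section 8.4.1 describing the proactive adverse event surveillance plan". Section 7.2 provides for reporting unanticipated problems, SAEs included, to the IRB, and for summarising notable non-serious events at continuing review. Section 6 contains no safety endpoint or safety analysis.

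**The concern.** The surveillance exists to find children who came to harm because they were not being monitored. A team activation is one way in which such harm shows itself. A transfer to the ICU arranged directly by the treating team is another, and it is not a trigger. If some transfers happen that way, the plan does not look for them, and the later steps (chart review, relatedness, suspension) depend on an event having been found.

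The pilot prepares for a cluster-randomized trial of the same strategy (sections 1.1 and 8.4.3.2). A statement that surveillance found no unmonitored deteriorations would reassure less than it seems to if one recognised route to the ICU had not been searched.

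**Working it through.** The plan states no safety figure, so there is nothing to reproduce. The check is to follow one kind of case through the text.

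**1. Two children compared.** Both deteriorate while unmonitored on a participating unit, and both go to the ICU. Team activation occurs for child A only.

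| Step in 8.4.1.2 | Condition | Child A | Child B |
|---|---|---|---|
| Trigger | team activation | yes | no |
| Chart review | trigger met | yes | no |
| Study adverse event | activation and unmonitored | yes | no |
| Relatedness and reporting steps | study adverse event | yes | no |

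The condition that matters clinically, being unmonitored at the time, is the same for both.

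**2. Other routes that might find child B.**

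- Section 7.1 points back to section 8.4.1 and adds no case-finding of its own.
- Section 7.2 is a reporting route. It works if someone notices the event and judges it to be an unanticipated problem or otherwise notable.
- Section 5.2.2 abstracts whether the child was in the ICU earlier in the admission. It is recorded only for eligible patients at data collection rounds. Child B appears only after returning to a ward, again meeting the criteria (including no supplemental oxygen or room air flow), and being present at a round. Rounds are targeted at least twice a week (section 4.2). The item does not separate a child transferred from the ward from one who began the admission in the ICU, and the plan does not link it to the safety review.
- Section 5.3 records monitoring status at the moment of a round, not at the time of a later event.

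So two routes might catch the case, and neither is designed to.

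**3. The protocol's own evidence.** Section 1.2.2 cites a quality improvement study that reduced time on continuous oximetry "without a difference in rapid response team activations, ICU transfers, or readmissions", and treats it as confirming safety. ICU transfer stands there beside activation as a separate outcome. Section 8.4.1.2 keeps the activation and leaves out the transfer.

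**4. Size.** Let D be the number of unmonitored deteriorations that end in an activation, an unplanned ICU transfer, or both, and q the share of these with a transfer but no activation. The present trigger finds D × (1 − q). The documents give neither D nor q and do not describe the sites' activation practice. At q = 0 nothing is lost, and the loss rises in proportion to q. No narrower range can be defended from the documents.

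**5. Counting patients.** Surveillance covers all bronchiolitis patients on participating units. The only planned patient count is of eligible children seen on rounds: at most 300 × 10 hospitals = 3,000 (section 3.3.2). Section 8.5 says that screening records nothing until a patient is found eligible and enrolled. Dividing surveillance events by the rounds count would therefore mix two populations. For x events in N admissions, the exact 95% limits are the 2.5% quantile of Beta(x, N − x + 1), taken as 0 when x = 0, and the 97.5% quantile of Beta(x + 1, N − x). The plan would supply x but not N.

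**The case against.** The case for leaving the plan alone has four parts.

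- **Other routes exist.** A reader might infer that such deteriorations are bound to be lost. The documents do not support that. Section 7.2 makes an ICU transfer reportable without any activation if it is judged an unanticipated problem, and section 5.2.2 will pick up some children who return to the ward. This stands, and it is why the point is limited to the proactive surveillance and to cases that may be missed.
- **The gap may be small.** Where ICU transfers from the ward normally involve a team activation, little or nothing escapes. This also stands. Any percentage for the shortfall would be a guess.
- **A rate is not an aim.** A reader might infer that, without a denominator, the safety evaluation fails. That goes too far. Sections 2 and 6 set no safety objective or endpoint, section 6 places little emphasis on power, and section 8.4.1.2 describes case-by-case detection and review, which needs no denominator. Nor could a rate show what the intervention did, since the study has a single arm and its rounds take place only during the intervention period. The denominator is therefore no more than an option.
- **The study is minimal risk.** Section 8.4.2 says so and notes that the primary team makes all monitoring decisions. This lowers the stakes. It does not explain why surveillance that the sponsor has chosen to run should leave out an outcome that its own cited evidence reports.

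**Conclusion.** The point holds for the trigger. As written, section 8.4.1.2 searches for harm only through team activations, and an unmonitored child transferred to the ICU without one may not be found. This rests on the text alone. It becomes a practical shortfall only if some unplanned transfers at participating hospitals occur without an activation. The documents neither state nor exclude this, so its size is unknown.

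It does not affect the primary questionnaire endpoints or the oximetry use rates, and it does not show that the study is unsafe. It is a gap in case-finding that is cheap to close. The missing count of admissions limits only how the events can be described.

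**What to change.** **Main change.** In section 8.4.1.2, add unplanned transfer from a participating unit to the ICU, in any bronchiolitis patient during the intervention period, as a further trigger for the existing chart review. Extend the study adverse event definition so that it covers a patient unmonitored at the time of the event that led to either an activation or such a transfer. Give a working definition of unplanned, and count an episode with both an activation and a transfer once. This alters surveillance only and sets no rule for patient care.

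**Cost.** Some additional chart reviews at each site. Their number cannot be estimated, because the documents give no frequency of ICU transfer. No new staff or type of procedure is needed.

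**Optional.** Ask each site for the number of bronchiolitis admissions to participating units during the intervention period, and report events, monitored and unmonitored, per 100 admissions with exact 95% confidence intervals. State two limits with the result: a single-arm rate cannot show an effect of the intervention, and the denominator includes children not eligible for data collection, such as those on oxygen, so it does not give a rate for stable children taken off monitoring.

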3 INVESTIGATIONAL PLAN

3.1 General Schema of Study Design

This is a pragmatic,²³ prospective, non-randomized, single-arm feasibility pilot implementation with the audit and feedback plus educational outreach intervention delivered at the hospital unit (i.e. ward) level.

This study does not directly involve making any changes to patient care – it only involves presenting data, guidelines, and evidence to clinical staff who make independent decisions about their own actions related to pulse oximetry monitoring in bronchiolitis. Any individual clinicians who do not wish

to participate may choose not to interact with the electronic communications and may choose to not attend meetings where this intervention is discussed.

On the Pragmatic-Explanatory Continuum,²³ this study is highly pragmatic for the following reasons (see cited article for detailed explanation of domains):

- **Eligibility criteria:** The same bronchiolitis patients who would likely be a candidate for the audit and feedback intervention if it was being provided in usual care are also eligible for this intervention since it is applied at the hospital unit level.
- **Recruitment:** The audit and feedback intervention will be delivered to the same health care professionals who are involved in the decisions or actions surrounding the initiation or discontinuation of continuous pulse oximetry monitoring in usual care.
- **Setting:** The pilot is being performed in hospital settings that are identical to the types of settings where we intend the results to be applied.
- **Organization:** Given the highly pragmatic nature of this study, the intervention will be delivered into each hospital using the same structures of care used locally for making improvements in bronchiolitis care delivery.

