3.3 Study Duration, Enrollment and Number of Sites

The intervention period will last between 2-4 months depending on the timing relative to the local epidemiology-dictated bronchiolitis season.

The primary subjects are hospital staff. Secondary subjects are patients age 2 through 23 months with a primary diagnosis of bronchiolitis.

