4 STUDY PROCEDURES

4.1 Pre-intervention period

- Implementation champions identified, local teams formed
- Local team members will meet with leadership on each potential unit; unit leadership will be given the opportunity to opt their unit out of the study for any reason.
- Implementation champions & teams perform educational outreach sessions on participating units
 - describing current guidelines
 - summarizing the evidence behind the guidelines
 - discussing potential alternatives to continuous pulse oximetry monitoring for patients in whom guidelines do not advise continuous pulse oximetry
- Distribution/dissemination of educational materials (e.g. slide presentations, posters, flyers, videos) to hospital staff working on study units focused on the bullet points above
 - materials collaboratively developed by the CHOP team and local implementation teams, with site-specific tailoring by the local implementation teams

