4.2 Intervention period

- Implementation teams will conduct data collection rounds and supplemental chart review (see Section 5) to determine continuous pulse oximetry status on bronchiolitis patients not receiving supplemental oxygen or room air flow, targeting data collection at least twice per week in order to acquire sufficient data for audit and feedback intervention.
- If any hospital staff responsible for the care of the patient are present and available on the unit, the data collector may perform real-time inquiry if feasible, briefly asking about the indications for monitoring individual patients, which will be documented in the study database as field notes without documenting any of the hospital staff member's identifiers.
- On a weekly basis, the data will be summarized in a dashboard and the dashboard along with the raw data will be returned to the site PI.
- Local implementation team will then share that data in electronic and in-person settings appropriate and tailored to each site (e.g. email, safety huddles,^{24,25} staff meetings, rounds, staff messages in electronic health record systems) with key clinician stakeholders who order or manage continuous pulse oximetry monitoring for bronchiolitis patients. Data will be contextualized with (a) the hospital's prior performance, (b) other hospitals' prior performance, (c) the current performance of other units in the same hospital, (d) the current performance of other units in other hospitals.
- Additional educational materials will be distributed and additional education/outreach sessions will be held by the local implementation team at a frequency determined by the site PI depending on local pulse oximetry use rates.

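### Active safety surveillance begins with the intervention period, but the educational part of the intervention reaches units earlier, so activations in between are not actively sought

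*Combined protocol and SAP*

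**What the plan says.** Section 3.1 describes an "audit and feedback plus educational outreach intervention delivered at the hospital unit (i.e. ward) level". Education is thus a component of the intervention.

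Section 4.1, on the pre-intervention period, states: "Implementation champions & teams perform educational outreach sessions on participating units". One listed topic of these sessions is "discussing potential alternatives to continuous pulse oximetry monitoring for patients in whom guidelines do not advise continuous pulse oximetry". Educational materials on the same topics also go to staff on study units in this period.

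Section 4.2, on the intervention period itself, states: "Additional educational materials will be distributed and additional education/outreach sessions will be held by the local implementation team".

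Section 8.4.1.2 explains why safety is evaluated: "since the intervention may lead to less intensive monitoring for some bronchiolitis patients". The search it sets up is for code blue and rapid-response "activations in all bronchiolitis patients hospitalized on units participating in the study during the intervention period". Charts of those patients are reviewed. An activation in a child who was unmonitored at the time counts as a study adverse event, whether or not it is related to the intervention.

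Section 7.1 states: "Clinical adverse events (AEs) will be monitored throughout the study". It then refers to 8.4.1 for the details. Section 7.2 covers reporting to the IRB of unanticipated problems that occur while the study is running.

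**The concern.** The plan's reason for watching activations is that the intervention could reduce monitoring. That reason applies from the moment staff first hear the message, which is at the outreach in section 4.1. The search opens only when the intervention period does.

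Take a code blue in an unmonitored infant a week after the first outreach session on a unit, with the intervention period not yet begun. A site following 8.4.1.2 as written would not list the event, would not review the chart, and would not classify it as a study adverse event.

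This matters because 8.4.1.2 is the only active search for patient harm that the document describes, and the study requests a waiver of patient consent (section 8.6.2). The authors also meant the search to be broad: it includes patients who were never seen on data collection rounds, because the intervention acts on the whole unit.

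**Working it through.** The plan gives no figure on this point, so there is none to reproduce. The check is mainly a comparison of sections.

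1. **Is education part of the intervention?** Yes. Sections 2.1 and 3.1 both define the strategy as audit and feedback together with educational outreach.
2. **When is it first delivered?** Before the intervention period, under section 4.1. Section 4.2 calls the later sessions and materials additional, so they are not the first exposure.
3. **What does the active search cover?** Only the intervention period (section 8.4.1.2).
4. **Does another section search actively before then?** No. Section 7.1 sends the reader back to 8.4.1. Section 7.2 is a reporting duty; it provides no activation listing and no review of whether the child was monitored.
5. **Could education alone change monitoring?** The document gives reason not to rule it out. Section 1.2.6 cites a review that places educational outreach among the most effective strategies. Section 1.2.2 describes a quality improvement bundle that included staff education and cut median monitored time from 10.7 to 3.1 hours. That bundle also had checklists and decision support, so it does not isolate education, and it showed no difference in rapid response activations, ICU transfers or readmissions.

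**Size, as an illustration only.** Section 3.3 states: "The intervention period will last between 2-4 months depending on the timing relative to the local epidemiology-dictated bronchiolitis season". The lead time from first outreach is not given, so it is assumed here.

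- p = weeks from first outreach to the start of the intervention period (assumed: 1, 2, 4 or 8)
- m = weeks in the intervention period: 2 × 52/12 = 8.67, or 4 × 52/12 = 17.33
- share of exposed calendar time without active search = p / (p + m)

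| p (assumed) | 2-month period | 4-month period |
|---|---|---|
| 1 week | 1/9.67 = 10.3% | 1/18.33 = 5.5% |
| 2 weeks | 2/10.67 = 18.8% | 2/19.33 = 10.3% |
| 4 weeks | 4/12.67 = 31.6% | 4/21.33 = 18.8% |
| 8 weeks | 8/16.67 = 48.0% | 8/25.33 = 31.6% |

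These are shares of calendar time, not of patients or events. They also treat a unit as fully exposed from its first session.

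**The case against.** **The study is low risk, and the window may be almost empty.** The intervention promotes existing guidelines, and section 3.3 ties the intervention period to the local season. If outreach is done before the season, few eligible infants are on the wards. This stands as a limit on the size of the gap. It does not remove the gap, because nothing requires outreach to finish before the season or to fall immediately before the intervention period.

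**Other routes exist.** An early event that came to someone's notice could still be reported under section 7.2, which is not confined to the intervention period. This also stands, but that route is passive.

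Three stronger readings are tempting, and the documents do not support them:

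- *That events after first exposure go uncounted in general.* All activations during the 2-4 month intervention period are sought and reviewed, and these too follow first exposure. Only the earlier window is affected.
- *That 7.1 and 8.4.1.2 flatly contradict each other.* Section 7.1 is a general statement that defers to 8.4.1. Section 3.3.1 gives staff participation as 2-4 months, the same as the intervention period, so the whole study could be read as that period. The wording is ambiguous and needs aligning.
- *That the later cluster-randomized trial would rest on this safety count.* No section says so. The pilot's purpose is feasibility, safety is not an endpoint, and section 6 plans no analysis of event rates.

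**Conclusion.** The point holds in a limited form. By the protocol's own definition, units are exposed to part of the intervention before active surveillance starts, and no section provides an active search for that interval. This follows from the text and rests on no assumption.

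The size of the gap is unknown. Across assumed lead times of 1 to 8 weeks it would be about 5% to 48% of exposed calendar time, but the share of missed events cannot be derived from the documents and would be small with pre-season outreach. This is a cheap improvement to the safety plan. It is not evidence that patients would be harmed, and it does not affect the questionnaire endpoints.

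**What to change.** In section 8.4.1.2, start surveillance on each unit at the date of its first educational outreach session or first distribution of educational materials, whichever is earlier, and continue it to the end of the intervention period.

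Record that start date for every unit. The delivery-event log in section 5.2.1 can hold it, with two provisos. The log must be opened before the intervention period, which the protocol does not currently say. It should also explicitly capture the distribution of materials such as posters and flyers, since its listed examples are sessions, emails and webinars.

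Reword section 7.1 so that it names the same window.

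The cost is an edit to two sections and a modest extension, at up to 10 hospitals, of the work already planned: listing activations, reviewing charts and, for qualifying events, speaking with staff.
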